7.5.3. Grade 4 Laboratory Abnormality or Clinical Event

- For a Grade 4 clinical event or clinically significant Grade 4 laboratory abnormality confirmed by repeat testing that is considered related to investigational medicinal product, investigational medicinal product will be permanently discontinued and the subject managed according to local practice. The subject should be followed as clinically indicated until the laboratory abnormality returns to baseline or is otherwise explained, whichever occurs first. A clinically significant Grade 4 laboratory abnormality that is not confirmed by repeat testing should be managed according to the algorithm for the new toxicity grade.
- Investigational medicinal product may be continued without dose interruption for a clinically non-significant Grade 4 laboratory abnormality (eg, Grade 4 CK after strenuous exercise, or triglyceride elevation that is nonfasting or that can be medically managed) or a clinical event considered unrelated to investigational medicinal product requires discussion with the Gilead Sciences Medical Monitor.

7.5.4. On-Treatment ALT Flare and Post-Treatment Exacerbation of Hepatitis B Management

In On-Treatment ALT Flare is defined as:

- Confirmed (within 3 days of receipt of initial laboratory results) serum ALT $> 2 \times$ Day 1 value and $>10 \times$ ULN, with or without associated symptoms.

7.5.4.1. Management of ALT Flare in Subjects Receiving Study Medication

If laboratory results indicate elevation of ALT $> 2 \times$ Day 1 value and $> 10 \times$ ULN, the following is recommended:

- Schedule the subject to return to the clinic as soon as possible (ideally within 3 days after initial laboratory results were drawn). During the visit, a clinical assessment of the subject will be performed. The assessment should include a physical examination and evaluation of the subject's mental status.
- If the ALT elevation is confirmed, request the central clinical laboratory to conduct reflex testing for plasma HBV DNA, HBV serology (HBsAg and HBsAb), HDV, HAV IgM, and HCV serology

Check the following laboratory parameters: serum ALT and AST, total bilirubin, INR, and serum albumin. Based on the results of the confirmatory tests, the following treatment modifications are recommended:

Elevated Liver Enzymes, Normal or Stable relative to Day 1 Liver Function Tests

If ALT levels are elevated (i.e., $> 2 \times$ Day 1 and $> 10 \times$ ULN) with normal or stable total bilirubin and INR relative to Day 1, the subject may remain on study medication and should be monitored weekly as long as ALT levels return to normal or Day 1 level. During monitoring, if the ALT values remain persistently elevated, the Investigator should discuss with the Gilead Medical Monitor whether the study drug should be discontinued.

Elevated Liver Enzymes, Elevated Liver Function Tests

If ALT values are elevated (i.e., $> 2 \times$ Day 1 and $> 10 \times$ ULN), and total bilirubin is confirmed to be $2 \times$ Day 1 value, and INR is 0.5 above Day 1, provided both are $> ULN$, the investigator should consider discontinuing study medication (upon discussion with the Gilead Medical Monitor, unless the safety of the patient is of immediate concern). The subject should be monitored weekly as long as ALT, total bilirubin, and INR values remain elevated or above Day 1 values.

During monitoring, if the ALT values and the liver function tests remain persistently elevated, the Investigator should discuss with the Gilead Medical Monitor whether the study drug should be discontinued.

7.5.4.2. Management of Exacerbation of Hepatitis B in Subjects who have Discontinued Study Medication

If laboratory results indicate (1) an ALT elevation $> 2 \times$ Day 1 and $> 10 \times$ ULN alone OR associated with (2) abnormal laboratory parameters suggestive of worsening hepatic function (total bilirubin $2 \times$ Day 1, INR 0.5 above Day 1, provided both are $>$ ULN) and the subject is on no post-study therapy for HBV, the following is recommended:

- Schedule the subject to return to the clinic as soon as possible (ideally no later than 3 days after the initial laboratory values were drawn). During the visit, perform a clinical assessment of the subject.
- Check the following laboratory parameters: serum ALT and AST, bilirubin, INR, and albumin.
- If the ALT elevation is confirmed, request the clinical laboratory to conduct reflex testing for plasma HBV DNA, HBV serology (HBsAg and HBsAb), HDV, HAV IgM and HCV. If serum HBV DNA is increasing, the investigator should consider immediate initiation of approved therapy.
- The subject should be followed until laboratory parameters (ALT, total bilirubin, INR) return to normal or Day 1 up to a maximum of 6 months after the initial occurrence of the event.

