Blood Urea Nitrogen	1.25 to 2.50 × ULN	> 2.50 to 5.00 × ULN	> 5.00 to 10.00 × ULN	> 10.00 × ULN
Hyperuricemia	>ULN to 10.0 mg/dL >ULN to 597 μmol/L	> 10.0 to 12.0 mg/dL > 597 to 716 μmol/L	> 12.0 to 15.0 mg/dL > 716 to 895 μmol/L	> 15.0 mg/dL > 895 μmol/L
Hypouricemia Adult and Pediatric ≥ 1 year	1.5 mg/dL to < LLN 87 μmol/L to < LLN	1.0 to < 1.5 mg/dL 57 to < 87 μmol/L	0.5 to < 1.0 mg/dL 27 to < 57 μmol/L	< 0.5 mg/dL < 27 μmol/L
Infant < 1 Year	N/A	1.0 mg/dl to <LLN- 57 μmol to <LLN	0.5 to < 1.0 mg/dL 27 to < 57 μmol/L	< 0.5 mg/dL < 27 μmol/L
Creatinine**	> 1.50 to 2.00 mg/dL > 133 to 177 μmol/L	> 2.00 to 3.00 mg/dL > 177 to 265 μmol/L	> 3.00 to 6.00 mg/dL > 265 to 530 μmol/L	> 6.00 mg/dL > 530 μmol/L

CHEMISTRY				
	Grade 1	Grade 2	Grade 3	Grade 4
Bicarbonate Adult and Pediatric ≥ 4 Years	16.0 mEq/L to < LLN	11.0 to < 16.0 mEq/L	8.0 to < 11.0 mEq/L	< 8.0 mEq/L
	16.0 mmol/L to < LLN	11.0 to < 16.0 mmol/L	8.0 to < 11.0 mmol/L	< 8.0 mmol/L
Pediatric < 4 Years	NA	11.0 mEq/L to < LLN 11.0 mmol/L to < LLN	8.0 to < 11.0 mEq/L 8.0 to < 11.0 mmol/L	< 8.0 mEq/L < 8.0 mmol/L
Triglycerides (Fasting)	NA	500 to 750 mg/dL 5.64–8.47 mmol/L	> 750 to 1200 mg/dL > 8.47–13.55 mmol/L	> 1200 mg/dL > 13.55 mmol/L
LDL (Fasting) Adult	130 to 160 mg/dL	>160 to 190 mg/dL	> 190 mg/dL	NA
	3.35 to 4.15 mmol/L	>4.15 to 4.92 mmol/L	>4.92 mmol/L	
LDL (Fasting) Pediatric >2 to <18 years	110 to 130 mg/dL	>130 to 190 mg/dL	> 190 mg/dL	NA
	2.84 to 3.37 mmol/L	>3.37 to 4.92 mmol/L	>4.92 mmol/L	
Hypercholesterolemia (Fasting)	200 to 239 mg/dL	> 239 to 300 mg/dL	> 300 mg/dL	NA
	5.16 to 6.19 mmol/L	> 6.19 to 7.77 mmol/L	> 7.77 mmol/L	
Pediatric < 18 Years	170 to 199 mg/dL 4.39 to 5.15 mmol/L	> 199 to 300 mg/dL > 5.15 to 7.77 mmol/L	> 300 mg/dL > 7.77 mmol/L	NA
Creatine Kinase	3.0 to < 6.0 × ULN	6.0 to < 10.0 × ULN	10.0 to < 20.0 × ULN	≥ 20.0 × ULN

* Calcium should be corrected for albumin if albumin is < 4.0 g/dL

** An overlap between the Grade 1 scale and the Lab's normal range for creatinine may result for Male subjects >70 yrs. Please follow the Gilead convention of grading any result within the LLN and ULN a 0.

ENZYMES				
	Grade 1	Grade 2	Grade 3	Grade 4
AST (SGOT)	1.25 to 2.50 × ULN	> 2.50 to 5.00 × ULN	> 5.00 to 10.00 × ULN	> 10.00 × ULN
ALT (SGPT)	1.25 to 2.50 × ULN	> 2.50 to 5.00 × ULN	> 5.00 to 10.00 × ULN	> 10.00 × ULN
GGT	1.25 to 2.50 × ULN	> 2.50 to 5.00 × ULN	> 5.00 to 10.00 × ULN	> 10.00 × ULN

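### For a confirmed, clinically significant, drug-related ALT above 10 × ULN and above 2 × Day 1, Section 7.5.3 mandates a permanent stop while Section 7.5.4.1 leaves the decision open, and the visible text does not say which governs

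*Protocol*

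**What the plan says.** Three parts of the protocol bear on the same laboratory result.

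- **Grading (Appendix 5, Enzymes).** The ALT row, from Grade 1 to Grade 4, reads "ALT (SGPT) 1.25 to 2.50 × ULN > 2.50 to 5.00 × ULN > 5.00 to 10.00 × ULN > 10.00 × ULN". ALT above 10 × ULN is therefore Grade 4, and ALT above 5 and up to 10 × ULN is Grade 3.
- **General toxicity rules (Sections 7.5.2 and 7.5.3).** For a "clinically significant Grade 4 laboratory abnormality confirmed by repeat testing that is considered related to investigational medicinal product, investigational medicinal product will be permanently discontinued". The product "may be continued without dose interruption for a clinically non-significant Grade 4 laboratory abnormality"; the examples given are creatine kinase after exercise and triglycerides. One grade lower, Section 7.5.2 requires that product be withheld for a related, confirmed, clinically significant Grade 3 abnormality until it falls to Grade 2.
- **ALT flare rules (Sections 7.5.4 and 7.5.4.1).** The flare definition begins "Confirmed (within 3 days of receipt of initial laboratory results) serum ALT" and sets the level at more than 2 × Day 1 and more than 10 × ULN. For a flare in which bilirubin and INR are normal, or stable against Day 1, "the subject may remain on study medication", with weekly monitoring. If ALT then stays high, the investigator discusses with the medical monitor whether to stop. If bilirubin and INR are both raised to the stated limits, "the investigator should consider discontinuing study medication", after discussion with the medical monitor unless safety is an immediate concern.

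**The concern.** A site with a subject in this ALT range can open the protocol at two places and find two different instructions. One mandates a permanent stop once the event is judged related. The other permits continuation, or asks only that stopping be considered, and does not ask about relatedness at all. Two investigators with the same result could act differently, and each could be cited as deviating from the section the other followed.

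The stakes are subject safety and uniform conduct. Section 7.5.5 names hepatobiliary toxicity as a potential risk of the study drug and describes the risk to humans at the clinical dose as unknown. The ambiguity also matters in the other direction. Subjects coinfected with hepatitis B may enroll (exclusion criterion 14 bars only those with HBV DNA above 9 log IU/mL), and Section 7.5.4.2 provides for exacerbation of hepatitis B after study drug is stopped.

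**Working it through.** No sample size, power or alpha is involved, so the check compares thresholds and then actions.

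**1. Do the two sections cover the same results?**
Grade 4 ALT is above 10.00 × ULN (Appendix 5); the flare level is above 10 × ULN (Section 7.5.4). The ULN cut-offs are identical. Both sections also need confirmation: Section 7.5 asks for repeat testing within 3 calendar days of receipt of results, and the flare definition asks for confirmation within 3 days of receipt.

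The flare has one further condition, ALT above 2 × Day 1. Write Day 1 ALT as d × ULN. The flare then requires ALT above max(10, 2d) × ULN.
- Inclusion criterion 7 limits ALT to 5 × ULN at screening.
- If d is also at most 5 (an assumption, because the limit applies at screening and not on Day 1), then 2d ≤ 2 × 5 = 10 and max(10, 2d) = 10.
- Under that assumption every ALT above 10 × ULN meets both flare conditions. If d exceeds 5, results between 10 and 2d × ULN fall under Section 7.5.3 alone.

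The overlap is therefore complete, or nearly so.

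**2. What does each section require for a confirmed, clinically significant, related result in the overlap?**

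| Finding | Section 7.5.3 | Section 7.5.4.1 |
|---|---|---|
| Bilirubin and INR normal or stable | Permanent stop, mandatory | May stay on drug, weekly monitoring |
| Bilirubin and INR both raised | Permanent stop, mandatory | Stopping to be considered |
| ALT persistently high | Already stopped | Discuss stopping with medical monitor |

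The actions differ in every row.

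**3. Does the ordering hold across grades?**
For a related, confirmed, clinically significant ALT above 5 and up to 10 × ULN, Section 7.5.2 mandates withholding. Above 10 × ULN, with bilirubin and INR normal or stable, Section 7.5.4.1 permits continuation. Taken together, the lower result triggers a mandatory interruption and the higher one need not.

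**4. Does the text limit Section 7.5.4.1 or rank the sections?**
- Neither the flare definition nor Section 7.5.4.1 mentions causality or restricts itself to coinfected subjects. Section 7.5.4.2, by contrast, names hepatitis B in its title and applies to subjects not on HBV therapy after the study.
- The opening of Section 7.5 places all clinical and clinically significant laboratory toxicities under one set of guidelines in Appendix 4. Section 7.5.5 refers graded abnormalities back to Section 7.5 as a whole, which contains both rules.
- Only the heading of Appendix 4 is visible in the text available, so an exception or ranking there cannot be excluded.

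**The case against.** The strongest reply is that the two sections can be read in sequence. Section 7.5.4.1 is framed as a recommendation and directs a search for cause (HBV DNA and serology, HDV, HAV IgM, HCV). Section 7.5.3 takes over once the event is judged related. On this reading the fault is unstated precedence, and no site is forced into contradiction. A second reply is that the heading of Section 7.5.4 mentions hepatitis B, the reflex tests are viral, and drug-caused hepatobiliary toxicity has its own Section 7.5.5, so Section 7.5.4.1 was meant for viral flares. A third is that an isolated ALT rise might be judged clinically non-significant.

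These are plausible intentions, but the visible text states none of them. In the heading, hepatitis B is attached to post-treatment exacerbation, and a viral work-up is a reasonable search for cause in any subject. A recommendation that permits continuation still conflicts with a mandatory stop unless something ranks the two. The non-significance route cannot explain why stopping is only to be considered when bilirubin and INR are raised as well.

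What stands is that the conflict is narrower than a quick reading suggests. It needs clinical significance, confirmation, relatedness and ALT above 2 × Day 1, and the permission to continue applies only with normal or stable bilirubin and INR. Appendix 4 may also resolve it.

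A reader might go further and infer a threat to the primary endpoint. The documents do not support that. Under the snapshot algorithm (protocol Section 8.5.1.2), stopping for an adverse event places a subject in the no-virologic-data category only if there is no on-treatment HIV-1 RNA in the Week 48 window. Treatment was double-blind, nothing suggests that inconsistent stopping would differ by arm, and the SAP (Sections 2.2.1 and 6) records the Week 48 analysis as already done. Nor do the Phase 2 data in Section 1.2.3.3 give a usable frequency: the only Grade 4 laboratory abnormalities were creatine kinase, and the reported Grade 3 ALT arose with alcohol abuse.

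**Conclusion.** The point holds in this limited form. For a confirmed, clinically significant, related ALT above 10 × ULN and above 2 × Day 1, the protocol gives a mandatory instruction in one section and a discretionary one in another, and the Grade 3 rule in Section 7.5.2 makes the sequence harder to follow. This is an inconsistency in the text as written, not merely missing detail.

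Its size cannot be expressed as a number: it applies to every subject who meets those conditions, and the documents give no basis for predicting how many. The claim that the overlap is complete rests on Day 1 ALT being at most 5 × ULN. The claim that no precedence is stated rests on the visible text only and is subject to Appendix 4. The grounds are patient safety and uniform conduct across sites. No view is taken on which clinical rule is right.

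**What to change.** Check Appendix 4 first. Then reconcile Sections 7.5.2, 7.5.3, 7.5.4.1 and Appendix 4 by stating:

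1. to whom Section 7.5.4.1 applies: all subjects, or only those with hepatitis B coinfection;
2. whether it applies when the event is considered related to study drug;
3. which section governs when both apply.

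The clinical content of the rule is for the sponsor's medical team to settle.

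The cost is a few sentences in an amendment or a letter to sites, with no change to data collection or analysis. The SAP for the final analysis was signed in September 2021, so a clarification can guide conduct only for subjects still on study drug. Beyond them, it would help in interpreting liver-related discontinuations in the final report and prevent the same wording from being carried into later protocols.

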7.5.5. Management of Potential Hepatobiliary Toxicity

Monkeys given a high dose (1000 mg/kg/day) for 39 weeks had evidence of biliary hyperplasia and hepatocyte hypertrophy on histopathologic examination. The risk to humans given the clinical dose of GS-9883 (50 mg/day) is unknown. Investigators should be aware of this potential toxicity. Any study subject exhibiting signs/symptoms or laboratory abnormalities suggestive of possible hepatobiliary toxicity should undergo thorough examination and clinical workup as deemed appropriate by the Investigator, and the Investigator must communicate promptly with the Gilead Medical Monitor. Consideration should be given to appropriate imaging studies (for example, ultrasound of the liver and biliary tree) and potential consultation with a gastroenterologist with specialty training in hepatobiliary diseases. Management of graded laboratory and clinical abnormalities will be managed as outlined in Section 7.5.

7.5.6. On-Treatment Hepatitis C Management

If a subject tests positive for HCV RNA at screening or develops signs or symptoms of active Hepatitis C virus Gilead recommends that local medical practice is followed at the discretion of the Investigator. Investigational medicinal product may be continued without dose interruption. Should the Investigator decide to initiate Hepatitis C treatment the Investigator must contact the Gilead Medical Monitor to confirm that no drug-drug interactions are expected. Subjects should return to the clinic for scheduled or unscheduled follow up visit(s) according to local medical practice for laboratory evaluations. If Hepatitis C treatment is initiated, Investigators should use the Gilead provided retest laboratory kits to manage the active Hepatitis C.

7.6. Special Situations Reports

7.6.1. Definitions of Special Situations

Special situation reports include all reports of medication error, abuse, misuse, overdose, reports of adverse events associated with product complaints, reports of adverse reactions in infants following exposure from breastfeeding, occupational exposure with an adverse event, and pregnancy reports regardless of an associated AE.

Medication error is any unintentional error in the prescribing, dispensing, or administration of a medicinal product while in the control of the health care provider, subject, or consumer.

Abuse is defined as persistent or sporadic intentional excessive use of a medicinal product by a subject.

Misuse is defined as any intentional and inappropriate use of a medicinal product that is not in accordance with the protocol instructions or the local prescribing information.

An overdose is defined as an accidental or intentional administration of a quantity of a medicinal product given per administration or cumulatively which is above the maximum recommended dose as per protocol or in the product labelling (as it applies to the daily dose of the subject in question). In cases of a discrepancy in drug accountability, overdose will be established only when it is clear that the subject has taken the excess dose(s). Overdose cannot be established when the subject cannot account for the discrepancy except in cases in which the investigator has reason to suspect that the subject has taken the additional dose(s).

Product complaint is defined as complaints arising from potential deviations in the manufacture, packaging, or distribution of the medicinal product.

7.6.2. Instructions for Reporting Special Situations

7.6.2.1. Instructions for Reporting Pregnancies

The investigator should report pregnancies in female study subjects that are identified after initiation of study medication and throughout the study, including the post study drug follow-up period, to Gilead PVE using the pregnancy report form within 24 hours of becoming aware of the pregnancy.

The subject's treatment assignment will be unblinded by the Investigator as described in Protocol Section 5.1.1.

Refer to below and the eCRF completion guidelines for full instructions on the mechanism of pregnancy reporting.

The pregnancy itself is not considered an AE nor is an induced elective abortion to terminate a pregnancy without medical reasons.

Any premature termination of pregnancy (e.g., a spontaneous abortion, an induced therapeutic abortion due to complications or other medical reasons) must be reported within 24 hours as an SAE. The underlying medical reason for this procedure should be recorded as the AE term.

A spontaneous abortion is always considered to be an SAE and will be reported as described in Section 7.3. Furthermore, any SAE occurring as an adverse pregnancy outcome post study must be reported to Gilead PVE.

The subject should receive appropriate monitoring and care until the conclusion of the pregnancy. Any complications during pregnancy and the outcome should be reported to Gilead PVE using the pregnancy outcome report form. If the end of the pregnancy occurs after the study has been completed, the outcome should be reported directly to Gilead PVE. Gilead PVE contact information is as follows:

Email: PPD and Fax: PPD

Pregnancies of female partners of male study subjects exposed to Gilead or other study drugs must also be reported and relevant information should be submitted to Gilead PVE using the pregnancy and pregnancy outcome forms within 24 hours. Monitoring of the subject should continue until the conclusion of the pregnancy. If the end of the pregnancy occurs after the study has been completed, the outcome should be reported directly to Gilead PVE, fax number PPD or email PPD

Refer to [Appendix 7](#) for Pregnancy Precautions, Definition for Female of Childbearing Potential, and Contraceptive Requirements.

7.6.2.2. Reporting Other Special Situations

All other special situation reports must be reported on the special situations report form and forwarded to Gilead PVE within 24 hours of the investigator becoming aware of the situation. These reports must consist of situations that involve study IMP and/or Gilead concomitant medications, but do not apply to non-Gilead concomitant medications.

Special situations involving non-Gilead concomitant medications does not need to be reported on the special situations report form; however, for special situations that result in AEs due to a non-Gilead concomitant medication, the AE should be reported on the AE form.

Any inappropriate use of concomitant medications prohibited by this protocol should not be reported as “misuse,” but may be more appropriately documented as a protocol deviation.

Refer to Section [7.6.2.1](#) and the eCRF completion guidelines for full instructions on the mechanism of special situations reporting.

All clinical sequelae in relation to these special situation reports will be reported as AEs or SAEs at the same time using the AE eCRF and/or the SAE report form. Details of the symptoms and signs, clinical management, and outcome will be reported, when available.

8. STATISTICAL CONSIDERATIONS

8.1. Analysis Objectives and Endpoints

8.1.1. Analysis Objectives

The primary objective of this study is to evaluate the efficacy of a FDC of GS-9883/F/TAF versus DTG + F/TAF in HIV-1 infected, antiretroviral treatment naïve-adult subjects as determined by the achievement of HIV-1 RNA < 50 copies/mL at Week 48

- The secondary objectives of this study are to evaluate the efficacy, safety and tolerability of the two treatment groups through Weeks 48, 96, and 144.
- To evaluate the long term efficacy and safety of FDC GS-9883/F/TAF through OL Weeks 48 and 96.

8.1.2. Primary Endpoint

The primary endpoint is the proportion of subjects who achieve HIV-1 RNA < 50 copies/mL at Week 48 as defined by the US FDA-defined snapshot algorithm.

